**Statistical Methods:**

All safety data will be summarized as described in the ZX008-1503 protocol and associated Statistical Analysis Plan. Efficacy analyses for sub-study participants that rely on the ERT seizure diary or that are specific to the Embrace watch will not be included in the main ZX008-1503 analyses. Exploratory data for the Embrace watch system data will be processed as follows:

- Embrace's automated convulsive seizure detection results will be manually compared to the diary counts of convulsive seizures. Cohen's Kappa values will be computed for agreement.

- The above will be repeated separately for events during periods of sleep vs. events while awake, based on Embrace’s determination of sleep/wake (periods of sleep will be based on actigraphy and EDA as measured by the Embrace watch).
- For each seizure detected by the Embrace watch, the peri-ictal EDA recording will be segmented from 60 minutes before detected seizure onset to 120 minutes afterward. A “significant EDA response” is declared when an increase in skin conductance level of more than 2 times the standard deviation of the pre-ictal baseline occurs. Significant EDA responses will be analyzed in terms of the amplitude of their EDA\_peak, the response duration, defined as the difference between “EDA\_end” and “EDA\_start,” and the natural logarithm of the area under the curve (AUC) of the rising phase (from “EDA\_start” to “EDA\_peak”) and of the total response (from “EDA\_start” to “EDA\_end”), ie, LogAUCrise and LogAUCtot. These measures will be examined to see if they vary over time with the treatment.
- Skin-surface temperature changes will be averaged daily and compared over time, with separate comparisons made for “seizure-free” periods and for “pre-seizure periods.” The duration of these periods will be based on average 60-minute intervals, but may also be examined with shorter intervals.
- Each episode of fever, defined as any body temperature above 98.6°F (37°C), and number, severity, and duration of each seizure detected by Embrace will be correlated to dose of study drug.

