#### **8.4 STATISTICAL METHODS**

All safety data will be summarized as described in the main Study ZX008-1503 protocol and associated Statistical Analysis Plan. Efficacy analyses for sub-study participants that rely on the ERT seizure diary or are specific to the Embrace will not be included in the main Study ZX008-1503 analyses. Exploratory data for the Embrace watch system data will be processed as follows:

Continuous data will be summarized using descriptive statistics including means, standard deviations, medians, lower and upper quartiles, and ranges. Categorical variables will be summarized with frequencies and percentages. Confidence intervals will be calculated for key parameters or estimates as warranted.

A complete description of the statistical analyses and methods will be available in the Statistical Analysis Plan, which will be finalized before the database is locked.

The primary analysis will rely on descriptive statistics to summarize responses to the Ease of Use Questionnaire from each time point where the questionnaire is administered. In particular, the modal, ie, most frequent, response to each item on the questionnaire will be reported at each time point. Responses across all items on the questionnaire will be summed to create an overall index that will also be reported at each time point.

Exploratory data for the Embrace watch system data will be processed as follows:

- Embrace’s automated convulsive seizure detection results will be manually compared to the diary counts of convulsive seizures. Spearman rank correlation will be used to quantify agreement.
- The Spearman rank correlation described above will be repeated separately for events during periods of sleep and for events while awake, based on Embrace’s determination of sleep/wake (periods of sleep will be based on actigraphy and EDA as measured by the Embrace watch).

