- For each seizure, the peri-ictal EDA recording will be segmented from 60 minutes before detected seizure onset to 120 minutes afterward. A “significant EDA response” is declared when an increase in skin conductance level of more than 2 times the standard deviation of the pre-ictal baseline occurs. The time of the beginning of such an EDA response is defined as “EDA\_start,” the time of the maximum peak of the EDA response is defined as “EDA\_peak,” and the point in time following this peak, when the EDA falls below 10% of the peak amplitude is defined as “EDA\_end.” Significant EDA responses will be analyzed in terms of the amplitude of their EDA\_peak, the response duration, defined as the difference between “EDA\_end” and “EDA\_start,” and the natural logarithm of the area under the curve (AUC) of the rising phase (from “EDA\_start” to “EDA\_peak”) and of the total response (from “EDA\_start” to “EDA\_end”), ie, LogAUCrise and LogAUCtot. These measures will be examined to see if they vary over time with the treatment. Each of the measures will be evaluated for changes over time using a mixed model repeated measures (MMRE) that allows for a different intercepts for each subject (ie, a random effect) but a common slope over time (ie, a fixed effect).
- Skin-surface temperature changes will be averaged daily and compared over time, with separate comparisons made for “seizure-free” periods and for “pre-seizure periods.” The duration of these periods will be based on average 60-minute intervals, but may also be examined more with shorter intervals. Changes in skin-surface temperature over time will be evaluated using similar MMREs as described above for EDA endpoints.

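### The EDA trend is measured only as peak and AUC in responses above 2 baseline SDs, which can understate a true fall; the common-slope model understates uncertainty if subjects' slopes differ (low priority)

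*Combined protocol and SAP*

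**What the plan says.** The secondary objective (section 2.2) and the evaluation criterion (section 8.3.2) concern the size of the EDA response in convulsive seizures, with no threshold attached.

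Section 8.4 cuts out a recording from 60 minutes before to 120 minutes after each detected onset. It calls a response significant when "an increase in skin conductance level of more than 2 times the standard deviation of the pre-ictal baseline occurs". Size is then taken only from those: "Significant EDA responses will be analyzed in terms of the amplitude of their" peak, their duration, and "the natural logarithm of the area under the curve (AUC) of the rising phase" and of the total response. The synopsis has the same restriction and ends with "These measures will be examined to see if they vary over time with the treatment".

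The trend model has "a different intercepts for each subject (ie, a random effect) but a common slope over time (ie, a fixed effect"). Temperature follows: "Changes in skin-surface temperature over time will be evaluated using similar MMREs as described above for EDA endpoints".

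Two sentences limit how much is fixed: "Confidence intervals will be calculated for key parameters or estimates as warranted", and "A complete description of the statistical analyses and methods will be available in the Statistical Analysis Plan", which is to be finalised before database lock.

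**The concern.** Whether a seizure is analysed depends on the outcome being analysed. If responses shrink, some drop below the threshold and leave, and those that stay are the larger ones. The peak has a second weakness: the maximum of a noisy signal stays above zero even when the underlying response is small, so it cannot fall in proportion. Both routes blunt the direction of change that the objective asks about.

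The threshold also moves with the baseline SD. That it is each seizure's own baseline is an inference from the per-seizure segmentation, though the natural one. If baseline SD changes over time, the bias can be offset, reversed or increased. A flat or weakly falling slope could therefore reflect the response itself, the baseline, the set of seizures retained, or the noise floor. Section 8.4 names no output that separates these.

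The slope model raises a different issue. Dose is titrated individually (section 3.1), so different time courses are plausible. If they occur, a model with random intercepts only ignores one source of variation in the average slope, and its interval is too narrow.

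**Working it through.** The plan gives no response size, baseline SD, seizure count, effect size or alpha for these analyses. There is no planned figure to reproduce, and every input below is an assumption. Only the 20 subjects (section 3.2), the 12 weeks (section 3.3) and the 2-SD rule come from the documents.

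**1. Selection alone, amplitude measured without noise.** Let log response be normal with SD s, let p0 be the share significant at the start, and let the true response be multiplied by f with baseline SD stable. Put z0 = Φ⁻¹(p0) and z1 = z0 + ln(f)/s. The ratio seen for raw amplitude is f × [Φ(z1+s)/Φ(z1)] ÷ [Φ(z0+s)/Φ(z0)].

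For a true 50% fall (f = 0.5):

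| s | p0 | z0 | z1 | Ratio seen | Fall seen | Share significant after |
|---|---|---|---|---|---|---|
| 0.7 | 70% | 0.524 | -0.466 | 0.5 × 1.848/1.271 = 0.727 | 27% | 32% |
| 1.0 | 95% | 1.645 | 0.952 | 0.5 × 1.175/1.048 = 0.560 | 44% | 83% |
| 0.7 | 99% | 2.326 | 1.336 | 0.5 × 1.077/1.009 = 0.534 | 47% | 91% |
| 1.0 | 99% | 2.326 | 1.633 | 0.5 × 1.050/1.010 = 0.520 | 48% | 95% |

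- Over s = 0.7-1.0 and p0 = 70-95% the range is 27-44% raw and 23-39% on the log scale. A true 30% fall appears as 17-27% raw.
- For log-AUC correlated 0.5-0.8 with log amplitude, a 50% fall appears as 29-45%.
- At p0 = 99% the median response is 2·exp(2.326s), about 10-20 baseline SDs, and the error is small (44-46% on the log scale).
- If baseline SD halves with no true change, there is a false fall of 4-17% raw. If baseline SD rises 30%, a true 50% fall appears as 13-40% raw.

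A simulated random-intercept fit with additive normal responses and a true 30% fall agrees. The slope among significant responses is 37%, 49%, 62% and 86% of the true one at mean starting responses of 2, 3, 4 and 6 SDs, with no material loss at 10.

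**2. Noisy trace.** One value per minute, 60 minutes before and 60 after onset, autocorrelated noise (0.5 or 0.9) with SD 1, a 5-minute rise, decay with time constant 20 minutes, lognormal amplitude (log-SD 0.7 or 1.0). Fall seen for a true 50% fall:

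| Median response | Peak, 2-SD filter | Peak, all seizures | Window mean, all seizures |
|---|---|---|---|
| 1.5-5 SD | 17-42% | 19-45% | 49-52% |
| 10-20 SD | 46-50% | 46-50% | 49-51% |

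At 1.5-5 SD, removing the filter recovers only about 0-5 points. The underlying fall among retained seizures is 46-50%, so most of the error there is the noise floor of the peak. The share significant falls only from 80-99% to 68-97%. With baseline SD halved and no true change, the filtered peak shows a false fall of 6-28%; the window mean shows -1 to 1%.

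**3. Common slope.** Take 20 subjects, 20 seizures each, times uniform over the 12 weeks (scaled 0 to 1), residual SD 0.8 and slope SD τ in log units per 12 weeks. Within-subject time information is 20 × 19/12 = 31.67. The true variance of the mean slope is about 0.64/31.67 + τ²/20. The model reports about (0.64 + τ²/12)/31.67.

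- τ = 0.4: true 0.0282, reported 0.0206, SE ratio 0.855. The effective cut-off is 1.96 × 0.855 = 1.68, so about 9% of intervals miss a true zero slope.
- τ = 0.6: true 0.0382, reported 0.0212, SE ratio 0.744, cut-off 1.46, about 14% misses.

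Simulation (2,000 trials per case, even to uneven seizure counts) gives 4-5% at τ = 0, 6-8% at 0.2, 10-13% at 0.4 and 15-22% at 0.6. Shorter repeat runs gave 8.4-9.3% at 0.4 and 12.4-13.0% at 0.6. With 8 seizures each the rates are 5%, 6-7%, 8-9% and 11-13%. In a separate simulation with other inputs, adding a random slope brought 7.0-26.3% down to 3.7-6.7%. Jackknife clustered standard errors with t on 19 df gave 4.3-7.3%. Temperature has the same structure but is not quantified, because its day-to-day autocorrelation is not given.

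**The case against.** The strongest objection concerns cause. A reader might infer that the 2-SD filter is what hides a fall, and that dropping it would cure the problem. The noisy-trace results do not support that: with small responses the unfiltered peak is almost as biased as the filtered one. Selection dominates only if amplitude is measured nearly without noise, and the documents do not say whether the signal is smoothed. This objection stands, and the point is worded accordingly.

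Second, the size is unknown. If responses are typically 10 SD or more there is little to correct, and a moving baseline SD removes any fixed direction. This also stands.

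Third, duration and the AUCs have no value without a response, so size given a response is a legitimate descriptive quantity. That is a reason to keep the analysis, but it does not answer the objective in section 2.2, which has no such condition.

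Fourth, one slope is a parsimonious choice for at most 20 subjects, and individual titration does not show that EDA slopes differ. A reader might infer that the model is invalid; it is valid if slopes are equal, and nothing in the documents shows otherwise.

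Fifth, the SAP is still to come, and section 8.4 already promises percentages for categorical variables. But section 8.4 fixes the filter and the slope structure, does not name the share significant over time, and a SAP that follows it inherits both features.

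**Conclusion.** The point holds in conditional form and is low priority: EDA and temperature are two of nine secondary exploratory criteria in a feasibility-sized pilot whose primary criterion is ease of use.

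The planned EDA measures can understate a true fall, through selection and through the noise floor of a maximum. Which dominates depends on signal noise and response size, which are not given. A true 50% fall appears as 27-44% under selection alone (70-95% significant at the start), as about 17-42% in a noisy trace at 1.5-5 SD, and as about 45-50% when responses are 10 SD or more or 99% are significant.

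The slope's standard error is too small only if slopes differ: about 8-13% misses at slope SD 0.4 and 12-22% at 0.6, with 20 subjects and about 20 seizures each. All these inputs are assumptions. The documents do not support saying that the analysis will miss a drug effect, or that its bias has a known direction.

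**What to change.** In section 8.4 and the synopsis, or in the SAP before it is finalised:

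1. Keep the significant-response analysis, labelled as a description of size given a response.
2. Add a baseline-corrected mean EDA change on the raw scale, over a fixed window (the seizure plus the post-ictal hour named in section 8.3.2), for every Embrace-detected convulsive seizure with EDA recorded. Base the conclusion on the section 2.2 objective on this. The raw scale allows zero and negative values. An all-seizure peak should not be used instead, because the noise floor remains.
3. Report the share of detected seizures with a significant response, and the pre-ictal baseline SD, over time as supporting descriptives. The share may move little and should not carry the conclusion.
4. Add a random subject slope with a small-sample correction to the EDA and temperature models. If it does not converge, use jackknife-type subject-clustered standard errors with t on subjects minus 1 df.
5. State as a limitation that the detector itself uses EDA (section 1.2), so low-EDA seizures may go undetected.

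The cost is SAP wording and some programming; Embrace data are already stored (section 9). Intervals will be wider. In the simulated trace the per-seizure coefficient of variation of the window mean is 1.0-1.2 times that of the filtered peak at median responses of 5-20 SD, and 1.3-2.9 times at 1.5-3 SD. The window mean does not protect against a drifting baseline or against selection by the detector. Added after database lock, these analyses would be post hoc.

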### **2.2 SECONDARY OBJECTIVES**

The secondary exploratory objectives of the study are:

- To compare objective convulsive seizure count, as captured by the Embrace, to convulsive seizure count captured manually in the electronic seizure diary.
- To compare objective convulsive seizure count during periods of sleep, as captured by the Embrace, to convulsive seizure count during periods of sleep captured manually in the electronic seizure diary.
- To examine if the size of the electrodermal activity (EDA) response during and after a convulsive seizure is reduced over time with ZX008 treatment.
- To examine if skin-surface temperature changes with ZX008 treatment.
- To examine if skin-surface temperature levels are different during periods of time preceding convulsive seizures than during times that are seizure-free.
- To examine correlation of study drug dose and fever-induced convulsive seizure frequency, severity, and duration.
- To examine the timing of diary-reported events vs. automatically detected events.
- To assess quality of life while using the Embrace system with the following measures:
  - Quality of Life (QoL) of the parent/caregiver using the EQ-5D-5L scale.
  - Affective symptoms of the parent/caregiver using the Hospital Anxiety and Depression Scale (HADS).
- To assess caregiver stress using the Perceived Stress Scale (PSS).

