### 3.2 NUMBER OF SUBJECTS

Up to 20 subjects from the main Study ZX008-1503 will have the option to participate in sub-study ZX008-1503-SS01 upon separate consent and fulfillment of entry criteria as detailed in Sections 4.1 and 4.2. Subjects will be approached sequentially until the target number of participants is reached.

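### The EDA trend model pools sleep and awake seizures; if their mix drifts, the slope could reflect that drift, so a state-adjusted slope belongs beside it

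*Combined protocol and SAP*

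**What the plan says.** Section 2.2 asks whether the size of the EDA "response during and after a convulsive seizure is reduced over time with ZX008 treatment".

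Section 8.4 takes the recording from 60 minutes before each detected onset to 120 minutes after it. A response counts as significant when "an increase in skin conductance level of more than 2 times the standard deviation of the pre-ictal baseline occurs". Four measures of each significant response are analysed: peak amplitude, duration, and the natural log of the area under the curve (AUC) for the rising phase and for the whole response. The section states the purpose: "These measures will be examined to see if they vary over time with the treatment". Each is fitted with a mixed model that "allows for a different intercepts for each subject (ie, a random effect) but a common slope over time (ie, a fixed effect"). No sleep/awake term, interaction or stratum is named there or in the Synopsis.

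The same section does use state for another purpose. The rank correlation between watch and diary counts "will be repeated separately for events during periods of sleep and for events while awake", and "periods of sleep will be based on actigraphy and EDA as measured by the Embrace watch".

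The design bears on this in three ways. All subjects receive ZX008 open-label and no comparator is described (3.1, 6.3). The sub-study is small and sized on feasibility (8.1): "Up to 20 subjects from the main Study ZX008-1503" (3.2). Wearing time is left to what each subject can manage by day and by night (4.1, item 1). Section 8.4 leaves the complete methods to a Statistical Analysis Plan to be finalised before database lock.

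**The concern.** A random intercept removes stable differences between subjects. It does not remove a change within a subject in the kind of seizure that enters the model, and there is no control arm in which the same drift would show.

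The mix of sleep and awake seizures could drift in two ways. Treatment might reduce one kind more than the other. Or the watch might come to be worn relatively more, or less, at night, so that the captured mix changes while the seizures themselves do not.

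A drift matters only if state affects the EDA measures. There are three reasons to think that it might:

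- The watch uses EDA to help tell sleep from wake, so background EDA is expected to differ by state.
- The 2-SD rule is set against the pre-ictal baseline, so state may influence which seizures enter.
- Section 8.4 does not say that peak and AUC are baseline-corrected. If they are not, background level enters the outcome directly.

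If both conditions held, a slope meant to describe the size of the response would partly describe when seizures occur or when the watch is worn. The error could go either way, including the decline that the objective looks for.

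**Working it through.** The plan gives no expected slope, effect size, SD, alpha or power for this analysis, so there is no figure to reproduce. What follows is illustration. The state difference, the drift in mix and the number of seizures per subject are assumptions.

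**Logged AUC measures.** Let r be the ratio of the geometric-mean response in sleep to that awake, and p the share of analysed seizures that begin in sleep. With no true change in either state, the mean log response is a constant plus p × ln(r). Over the period, then:

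apparent relative change = exp[(p_end − p_start) × ln(r)] − 1

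Example: r = 0.5 and a rise of 20 points give 0.2 × (−0.693) = −0.139, and exp(−0.139) − 1 = −12.9%.

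| Assumed r | +10 points | +20 points | +30 points |
|---|---|---|---|
| 0.5 | −6.7% | −12.9% | −18.8% |
| 0.7 | −3.5% | −6.9% | −10.1% |
| 1 | 0 | 0 | 0 |
| 1/0.7 | +3.6% | +7.4% | +11.3% |
| 2 (= 1/0.5) | +7.2% | +14.9% | +23.1% |

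A fall in the sleep share swaps each row with that of its inverse ratio.

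**Peak amplitude and duration.** Section 8.4 does not say that these are logged. On the original scale, with r now the ratio of arithmetic means, the relative change is (p_end − p_start)(r − 1) / [1 + p_start(r − 1)]. It depends on the starting share, so the table does not carry over.

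**Chance of a misleading trend.** A simulation used 20 subjects, 2,000 runs per scenario, subject-specific intercepts, a common slope and no true trend within either state. The slope was fitted by the within-subject estimator and tested two-sided at 5% (8.4 sets no level). Here d is the sleep-minus-awake difference in within-subject SDs, and the expected spurious change is d × (p_end − p_start).

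| d | Sleep share | Expected change (SD) | Significant, 10 seizures per subject | Significant, 30 per subject |
|---|---|---|---|---|
| 0.5 | 30% to 50% | 0.10 | 6.4% | 11.1% |
| 0.5 | 30% to 60% | 0.15 | 9.8% | 18.8% |
| 1.0 | 30% to 50% | 0.20 | 9.0% | 24.7% |
| 1.0 | 30% to 60% | 0.30 | 18.2% | 46.2% |
| −0.5 | 30% to 50% | −0.10 | 7.6% | 11.4% |
| −0.5 | 30% to 60% | −0.15 | 8.9% | 17.4% |

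With d = 0, or with the share constant at 40%, the rate was 4.2% to 6.4%, so the mildest row cannot be told from no bias. With a sleep/awake term in the model, the mean estimate was within about 0.01 SD of zero and the rate was 3.9% to 6.0% in every scenario. That is the best case for adjustment: state was recorded without error, its effect was additive, and the 2-SD rule was not simulated.

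**The case against.** **The ictal response is not shown to differ by state.** One might infer that the plan's own definition of sleep makes state a known source of variation in the response. It does not. Using EDA with actigraphy to find sleep points at most to a difference in background signal; the model concerns the rise around a seizure, judged against that seizure's own baseline. The rule that ends a response at 10% of peak amplitude also reads more naturally for a baseline-corrected signal, although correction is not stated. This objection stands: a difference by state is plausible, not established.

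**The overall slope answers a legitimate question.** The objective in 2.2 does not condition on state. If treatment changes the mix, the mix is a consequence of treatment, and a slope over all seizures describes the total change. Adjusting for state answers a different question. This stands too, and rules out replacing the planned slope. It has less force where the drift comes from wear, because then only the captured sample has changed.

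**State is itself partly EDA-based.** Adjustment could condition on the outcome signal. Classifying from pre-onset data reduces this but does not end it, since pre-onset EDA may also form the baseline. An actigraphy-only check is needed.

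**The stakes are modest and detail is deferred.** The analysis is secondary and exploratory, in a pilot whose primary analysis is descriptive and concerns ease of use. The later Statistical Analysis Plan may include the term, so its absence from 8.4 does not show that it was rejected. This limits the weight of the point, but the text available contains no commitment to it.

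**Conclusion.** The point holds conditionally. Section 8.4 pools sleep and awake seizures in the EDA trend although the plan already classifies events by state. If the response differs by state and the mix drifts, the common slope combines a change in response size with a change in mix. Under the assumed ratios and shifts, the logged AUC measures would show an apparent change of about −4% to −19%, or +4% to +23% with the inverse ratios. Remove either condition and there is no bias.

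A reader might conclude that the planned slope is biased, or that any shift in mix will pass for a change in EDA response. The documents support neither conclusion: they give no figure for the state difference or for the drift. What they support is that the planned output could not tell the two explanations apart. This is a cheap improvement, not a demonstrated error.

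**What to change.** Keep the planned overall slope for each EDA measure. In 8.4 and the Statistical Analysis Plan, add:

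1. A second slope from the same model with sleep/wake state at seizure onset as a fixed effect, reported beside the first.
2. State classified from data before onset, so that the seizure's own movement and EDA do not set it, with actigraphy-only classification as a sensitivity check.
3. The share of sleep-onset seizures in each 28-day period, so that a change in timing or capture is visible in its own right.
4. A reading rule: describe a trend as a changed EDA response only if it persists after adjustment.
5. A statement of whether peak amplitude and AUC are measured from the pre-ictal baseline.

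The cost is a small extra derivation, because 8.4 does not say that the watch's sleep/wake determination leaves out the seizure itself, and one more parameter per model with up to 20 subjects. No new data collection or subject procedure is needed.

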### **4.1 INCLUSION CRITERIA**

In addition to meeting all of the main Study ZX008-1503 inclusion criteria subjects in the sub-study must also be willing to wear and use the Embrace watch and parents/caregivers must be willing to use the Alert app. This includes:

1. Subject is willing to wear the Embrace watch on the wrist (alternatively ankle, if needed for younger children). Subjects are asked to wear the watch for as many hours of the day as possible and for the entire night, if possible, for the duration of the sub-study.
2. Subject's parent/caregiver is willing to use the Alert App and receive voice and SMS notifications on their personal smart-phone, and ensure the smart-phone has internet connectivity; iOS 8.2 or higher is required for iPhone users.
3. Subject/subject's caregiver is willing to ensure that the Embrace watch remains within close proximity of the paired iPod Touch running the Empatica Alert app.
4. Subject/subject's caregiver is willing to ensure that the Embrace system is properly stored when not in use, and is not left exposed to direct sunlight, moisture, humidity or rain while in storage. The Embrace watch is water resistant but should never be submerged in water. Bathing and/or showering with the watch is acceptable, however.
5. Subject/subject's caregiver is willing to regularly clean the Embrace watch, routinely inspect the watch for sharp edges and damage, and ensure the watch is never worn over damaged or broken skin.
6. Subject/subject's caregiver is willing to ensure that the Embrace system is properly charged daily during a time when the subject is being observed so any seizures that occur during times that the device is not being worn are able to be added to the record manually.

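### Daily mean skin temperature has no adjustment for which hours the watch was worn, so a drift in the day/night wear mix would enter the time slope

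*Combined protocol and SAP*

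**What the plan says.** Section 8.4 of the protocol gives the summary measure: "Skin-surface temperature changes will be averaged daily and compared over time". Seizure-free and pre-seizure periods are compared separately, and "The duration of these periods will be based on average 60-minute intervals, but may also be examined more with shorter intervals". The model follows: "Changes in skin-surface temperature over time will be evaluated using similar MMREs as described above for EDA endpoints". The EDA model has a random intercept for each subject and a single slope over time shared by all subjects.

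Section 4.1 leaves wear to the family: "Subjects are asked to wear the watch for as many hours of the day as possible and for the entire night, if possible". It also requires that the system be "properly charged daily during a time when the subject is being observed", and the same criterion recognises that the watch is off the body at times. Neither the clock time nor the length of charging is fixed.

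No section sets a minimum number of hours for a valid temperature day, a clock window, a weighting of day and night hours, or a rule for off-body readings. The only validity rule (section 8.2.2) asks for one week of valid seizure data per subject. Section 8.4 uses the Embrace sleep/wake classification, but only for seizure counts.

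**The concern.** With no rule stated, a daily average is naturally read as an average over the hours recorded that day. It then weights day and night by the hours worn in each. If the two differ in skin temperature, the daily mean depends on how the watch was worn as well as on the subject.

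A random intercept absorbs a stable wearing habit that differs between subjects. It does not absorb a change of habit within subjects that runs in step with study time, because study time is the only predictor described. A secondary objective in section 2.2 asks whether skin temperature alters on ZX008. The sub-study is open-label and uncontrolled, so no comparison group would show the same wear-driven slope and expose it.

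At stake is whether the reported slope describes the subjects' temperature or partly their wearing pattern.

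**Working it through.** The plan states no effect size, variability, alpha or power for temperature, so there is no figure of its own to reproduce. What follows is an illustration.

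**Inputs from the documents.** Up to 20 subjects (section 3.2); 12 weeks, i.e. 84 days (section 3.3); random intercept and common slope (section 8.4).

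**Assumptions not in the documents.** Night-minus-day skin temperature difference D = 0.5, 1 or 2 °C; night wear n = 10 h; day wear d starting at 12 h.

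**Shift in the daily mean.** With hours weighted equally,

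daily mean = day level + D × n/(n + d).

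The change when wear moves from (10, 12) to a new pattern is D times the change in n/(n + d):

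| New wear (night, day) | Change in night share | D = 0.5 | D = 1 | D = 2 |
|---|---|---|---|---|
| 10, 12 (no drift) | 0 | 0 | 0 | 0 |
| 10, 10 | 10/20 − 10/22 = 0.045 | +0.02 | +0.05 | +0.09 |
| 10, 8 | 10/18 − 10/22 = 0.101 | +0.05 | +0.10 | +0.20 |
| 10, 4 | 10/14 − 10/22 = 0.260 | +0.13 | +0.26 | +0.52 |
| 5, 12 | 5/17 − 10/22 = −0.160 | −0.08 | −0.16 | −0.32 |
| 0, 12 | 0 − 10/22 = −0.455 | −0.23 | −0.45 | −0.91 |

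Losing day hours raises the mean and losing night hours lowers it, given a warmer night.

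**Could the planned model mistake this for a trend?** A simulation set the true trend to zero, with 20 subjects, 84 daily values each, between-subject SD 0.5 °C, day-to-day SD 0.4 °C, and linear drift in day wear (daily SD 1.5 h) in every subject. It used a two-sided 5% test and 1,000 runs per scenario. Share of runs with a significant slope:

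| Day wear over 12 weeks | D = 0.5 | D = 1 | D = 2 |
|---|---|---|---|
| 12 h throughout | 4.9% | 4.3% | 4.8% |
| 12 to 10 h | 11% | 26% | 77% |
| 12 to 8 h | 31% | 86% | 100% |
| 12 to 4 h | 98% | 100% | 100% |

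A hand check on one cell: the sum of squared centred days is 84 × (84² − 1)/12 = 49,385 per subject, or 987,700 for 20. The standard error of the change from first to last day is 0.4 × 83/√987,700 = 0.033 °C. A shift of 0.101 °C is about 3.0 standard errors, which gives power near 86%.

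**With fixed weights.** Standardising each day to 10/24 night and 14/24 day gives a mean change of about 0.00 °C and 3.5% to 5.7% significant slopes in all 12 scenarios. This is expected, since fixed weights take the hours worn out of the daily value.

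**Off-body readings.** If they are logged and kept, each off-body hour in 24 lowers the mean by gap/24. For an assumed skin-to-room gap of 6 to 11 °C that is 0.25 to 0.46 °C. This is a shift in level; it contributes to the slope only if off-body hours change over the study.

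**The case against.** Five arguments on the other side have weight.

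- **The detail may come later.** Section 8.4 defers a complete description of methods to an SAP to be finalised before database lock, and no such text is in the documents. That the mean is taken over whatever hours were recorded is therefore an inference from silence. This stands as a limit. But 8.4 already fixes the summary measure and the model, and an SAP that follows them inherits the problem.
- **Nothing shows that wear will change.** A reader might infer that wear falls over the weeks, mostly by day. The documents report no wear pattern, so this is an assumption. Without drift there is no false trend. Drifts in opposite directions across subjects would also tend to cancel in a common slope.
- **Charging is not in itself a cause.** A reader might infer that the daily charging gap produces a trend. A constant gap shifts only the level, which the intercept takes up.
- **The off-body figures are not trends.** It is tempting to quote them as the size of the bias. They are level shifts, and no section says that the watch logs temperature when off the body.
- **The averaging may be by interval.** The separate seizure-free and pre-seizure comparisons use 60-minute intervals, so the averaged quantity may not be a whole-day mean. The intervals are not matched on time of day, however, and seizure-free intervals still come from the hours worn.

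The endpoint is also secondary and exploratory in a feasibility pilot, and section 7 excludes use of the signals for diagnosis or treatment. That limits the consequence; it does not make the slope interpretable.

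**Conclusion.** The point holds conditionally. As written, section 8.4 offers no protection against a systematic change in the mix of day and night hours worn. Such a change would appear as a temperature slope if skin temperature differs between day and night. On the assumptions shown, a fall in day wear from 12 to 8 h shifts the mean by about +0.05 to +0.20 °C over 12 weeks; loss of night wear shifts it the other way. The false-positive rates depend further on assumed SDs, on drift common to all subjects, and on a 5% test that the plan does not specify, so they show sensitivity and are not forecasts.

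The documents do not support saying that a wear-driven trend will occur, or in which direction. Nor would correcting for wear let the slope be credited to ZX008: there is no control arm, and dose is being titrated from the start of the extension (section 3.1). This is a worthwhile low-cost improvement to an exploratory analysis.

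**What to change.** In section 8.4 and the SAP:

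1. Average temperature within fixed clock blocks (for example four 6-hour blocks) or separately by Embrace sleep/wake state, instead of over the whole day.
2. Fit the same random-intercept, common-slope model to those means, with block or state as a fixed effect.
3. Exclude readings that can be identified as off-body, and state how they are identified.
4. Prespecify a minimum share of valid wear for a block to count. The documents suggest no value; 50% is a workable choice.
5. Report hours worn per study week, by block or state, beside the temperature trend, so that a reader can see whether wear drifted.

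The cost is SAP wording and programming. Embrace data are stored automatically (section 9), and the sleep/wake classification is already planned, so no visit or family burden is added. The downside is that poorly worn blocks are lost, and some drift in hours worn within a block can remain.
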